Study Rationale	While e-cigs are commonly represented as safer alternatives to tobacco cigarettes, little is known regarding the health effects of their short- or long-term use. The responses and the e-cig components exerting these effects on the airways are largely unknown. Hence, a critical need currently exists in identifying e-cig components, namely specific flavors, modifying respiratory immune responses.		
Study Objective(s)	Primary		
	• Determine the effects of CA-containing e-cigarettes on airway epithelial cell ciliary function (i.e. MCC) in vivo		
	Secondary		
	 Baseline differences in MCC in non-smokers/non-vapers as compared to e-cigarette users Differential cell counts in CA-induced changes in IS samples 		

• Regional lung clearance rates via MCC scan.

Test Article(s) (If Applicable)	An e-cigarette that contains CA-containing flavors.
Study Design	This will be a blinded, crossover study to assess the effect that vape liquid containing cinammaldhyde (CA) has on the innate mucosal immune system of current users of e-cigarettes. The primary endpoint will be the effect of the CA-containing e-cigarette liquid on airway epithelial cell ciliary function, in vivo. The primary analysis will be achieved via the mucociliary clearance (MCC) scan.
	Prior to enrollment, subjects will be screened based on their ability to produce sputum with sufficient viable cell counts for analysis as well as their history of radiation exposure. Study visits thereafter will include a baseline visit for both the vape/non-vape cohorts to measure baseline MCC, epithelial lining fluid (ELF), induced sputum (IS), blood values, and urine. The e-cigarette cohort will have a total of seven visits, and the control cohort with 3 visits.
Subject Population	Inclusion Criteria
	1. Subjects age 18-40

key criteria for Inclusion and Exclusion:	2. Subjects who currently use a vaping device and an equal number of subjects who do not use a vaping device		
	Exclusion Criteria		
	3. Any pre-existing lung disease (asthma, cystic fibrosis)		
	4. Any significant chronic illness, such as, but not limited to, heart disease, uncontrolled hypertension, diabetes, auto-immune disease		
	5. Any use of tobacco products (other than e-cig) in the past 3 months, or a greater than 10 pack year history of smoking cigarettes.		
	6. Pregnant or nursing women		
	 Subjects with a history of radiation exposure in the past year which exceeds annual safe limits. 		

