3.3 Study Duration, Enrollment and Number of Subjects 22 e-cig users, and 22 non-e-cig users will be recruited into the observational phase (stage 1) of the study. Each subject will have a screening visit followed by a baseline visit with an MCC scan. After the baseline/MCC scan visit, the subject will return within approximately 24 hours for a follow up MCC scan and a sputum induction. The non-e-cig users are completed at this point (note: data from 12 previously studies non-e-cig users will be included in the overall data analysis). The subject in the e-cig cohort will return the next day for a follow up scan/sputum induction as well as a training session with our e-cigarette device/lifeshirt. There will be a 2-6 week washout and then the vaping/MCC/SI session. The entire study should be concluded in no more than 3 years.

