3.4 Study Population

-Inclusion and Exclusion Criteria

Inclusion:

• Subjects who currently use a vaping device and an equal number of subjects who do not use a vaping device

• Age 18-40

• Subjects must have a FVC and FEV1 of at least 80% of predicted. Subjects who fall out of the normal range will be offered a copy of the test to share with their personal physician. Exclusion:

• Any pre-existing lung disease (asthma, cystic fibrosis, etc.)

• Any significant chronic illness, such as, but not limited to, heart disease, uncontrolled hypertension, diabetes, auto-immune disease

• Any use of tobacco products (other than e-cig) in the past 3 months, or a greater than 10 pack year history of smoking cigarettes.

- Pregnant or nursing women
- Subjects with a history of radiation exposure in the past year which exceeds annual safe limits.

STUDY PROCEDURES (what will be done)

Screening/Baseline Visit procedures:

Subjects will arrive for the screening and baseline visit. After informed consent is obtained, a medical history, including medication use and radiation history, will be obtained. Urine pregnancy tests will be obtained on all women, and must be negative. Urine will be collected for measures of cotinine and NNAL (both markers of nicotine). Spirometry will be collected, and subjects will undergo SI procedure. Subjects must produce an adequate sputum (based on cell counts and viability) in order to continue in the study. Subjects who vape will be given a daily diary to record information on the device and e-liquids (name/vendor/e-liquids/puffs/device settings) used during their normal vaping sessions for the entire duration of the study.

Subjects who successfully complete all screening procedures will return to the study lab and undergo a baseline MCC, 40cc of blood collection, epithelial fluid lining collection (ELF), urine collection, and an induced sputum (IS) procedure. Subjects will be asked to refrain from vaping for 12 hours prior to the MCC study. Subjects will return 24 hours later for a 30-minute follow up gamma camera scan and sputum induction Vital signs will be collected prior to and immediately after sputum induction. At this point, participation ends for all non-vaping subjects.

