For those who vape, at this point we will introduce the device and instruct the subject in the proper technique. Before the training session begins the subject will be fitted with a Lifeshirt vest (Vivometrics, Inc.) that will allow continuous measurements of breathing pattern (tidal volume, respiratory rate, flow, etc.) by respiratory inductance plethysmography. Measurements will be verified with the TSI Series 4000 mass flowmeter; this is a passive measurement that occur concurrently with the subject's inhalation. Pulmonary mechanics will be measured while the subject vapes with our device as well as their own e-cigarette device

The Vapor Shark DNA 250[™] and e-liquids are provided by us for the indicated vaping sessions. The subjects will be asked to follow a laboratory-based protocol involving 6, 5-minute paced vaping segments (1 puff/minute). This device is used allows manual control and recording of the vapor settings (voltage, wattage, puff volume, and puff frequency), using the myVapors[™] software. Data can be directly imported into a database, thus allowing detailed information of a very controlled vaping session.

3.5

Intervention/Treatment procedures (by visits):

For stage 2, subjects who are continuing in the study will return to the lab 2-6 weeks later for the MCC/vape session. Subjects will be assigned a treatment regimen based on the randomization scheme produced by the Study Coordinator. Subjects will be asked to refrain from vaping for 12 hours before this session. After vital signs, baseline spirometry, urine, and ELF collection, subjects will vape with the randomized e-liquid, either with or without CA. Ten minutes after completion of the vaping session, subjects will undergo MCC scan for 120 minutes followed by immediately by vital sign collection, ELF collection, spirometry, and IS. Vitals signs will be collected again prior to discharge. Subjects will return the next day for a 24-hour follow up scan followed by vital signs collection. Another IS, ELF, Urine, and blood collection will be conducted in the post-MCC/vape session. Vital signs collection will be repeated prior to discharge. There will a 2-6 week washout, and the subject will return to repeat the session, vaping the crossover e-liquid.

(2) Intervention: study intervention/experimental treatment.

Cinnamaldehyde (CA)-containing e-cigarettes versus e-cigarettes with other flavors, such as tobacco.

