5.3 Statistical Methods

Repeat measures of MCC in healthy nonsmokers have provided paired standard deviation data that establish confidence we can detect a significant change in MCC associated with the e-cig challenge. Similar to our previous studies (Bennett et al., 2014), repeat measures analysis will be used to assess differences in MCC between the three study days to determine CA-induced changes within each study subject. For the stage 1 studies, comparisons by ANOVA will also be done for baseline MCC values obtained in non-e-cig users each study day, to detect potential overall differences in MCC between e-cig users and non-users (both smokers and non-smokers). To control for confounding variables, such as age, BMI, and sex, we will include these variables as covariates in our multivariate analysis, similar to our previous study (Martin et al., 2016). Statistical analyses will be conducted in close collaboration with [name], Professor in Biostatistics, who leads the Biostatistic Core for the Center for Environmental Medicine Asthma, and Lung Biology (CEMALB), where this study will be conducted.

All statistical estimates (e.g. treatment effects, means, medians, mean differences, etc.) will be tabulated along with corresponding confidence intervals. [name], the leader of the biostatistics core for the CEMALB will lead the statistical team overseeing data analysis and guide the statistical analysis for this study. For all analyses described above a p-value of ≤ 0.05 is considered to be statistically significant. For data not statistically significant based on these criteria, they will be reported as "inconclusive".

For the Stage 2 studies, linear model methods for repeated measures will be used to evaluate the effect of CA-containing e-liquids on MCC and IS endpoints (e.g., immune cell function and inflammatory mediators).

For each outcome variable (e.g., total MCC) the dependent variable will be the post-vaping change from the baseline value that was obtained during the screening visit.

Models for MCC measures. For total MCC scores in Stage 2, $\Delta Y_{ij}(t)$ is the change-from-baseline score in the k-th period (k = 1, 2) from the i-th participant in the j-th treatment sequence (j = A:B, B:A). The primary analyses will focus a linear mixed-effects model for $\Delta Y_{ij}(t)$ conditional on the following explanatory variables: assigned treatment regimen, and period. For MCC scores, the model is

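### Section 5.3 takes the Stage 2 baseline from the screening visit, although baseline MCC and baseline sputum are collected at a later visit; it also labels the next-day sputum 48 h

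*Combined protocol and SAP*

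**What the plan says.** **Analysis rule.** Section 5.3 states, for every Stage 2 outcome and with total MCC as its example, that "the dependent variable will be the post-vaping change from the baseline value that was obtained during the screening visit".

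**Schedule.** The Synopsis (Study Design) has subjects screened first and then attend "a baseline visit for both the vape/non-vape cohorts to measure baseline MCC, epithelial lining fluid (ELF), induced sputum (IS), blood values, and urine". Section 3.3 agrees: "Each subject will have a screening visit followed by a baseline visit with an MCC scan". The screening and baseline procedures at the end of Section 3.4 (Study Population) say "Subjects who successfully complete all screening procedures will return to the study lab and undergo a baseline MCC"; blood, ELF, urine and induced sputum are taken at that same return visit. The Synopsis gives the totals: "The e-cigarette cohort will have a total of seven visits, and the control cohort with 3 visits".

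**Sputum at screening.** Sputum is also induced at screening, where it decides eligibility: "Subjects must produce an adequate sputum (based on cell counts and viability) in order to continue in the study".

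**Abstinence.** For the baseline visit: "Subjects will be asked to refrain from vaping for 12 hours prior to the MCC study". For the Stage 2 test days (Section 3.5, Intervention/Treatment procedures): "Subjects will be asked to refrain from vaping for 12 hours before this session". None is stated for the screening sputum.

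**Late sputum.** The immune cell model in Section 5.3, in both its text and its table, has a time point 48 hours after vaping. The Synopsis, Section 3.1, the intervention procedures and the follow-up procedures all put the late sample at about 24 hours or on the next day, and the follow-up section plans nothing after it.

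**The concern.** The rule defines the dependent variable of the Stage 2 models, so it should name a measurement that exists and is the intended reference. For MCC it names a visit without an MCC measurement. For sputum it names a real sample, but not the one that the rest of the protocol treats as baseline.

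What is at stake is the set of sputum change-from-baseline estimates. Section 5.3 lists μA (without CA) and μB (with CA) among the parameters to be interpreted, and Section 5.4 justifies the sputum sample size by a difference between baseline and treatment. Differential cell counts are a secondary endpoint and immune cell function is exploratory. If the screening sample is the reference, a change from baseline could partly reflect recent habitual vaping before screening, or selection of subjects on that sample, rather than the session.

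The 48 h label matters less. It gives the model terms δA and δB a time at which no sample is scheduled.

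**Working it through.** No sample size or power figure enters this point. The check compares the schedule with the analysis rule.

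**Step 1: are screening and baseline separate visits?** Reproduce the Synopsis totals.
- Vapers: 1 screening + 3 scan sessions × 2 days = 7. Controls: 1 screening + 1 session × 2 days = 3. Both match.
- If screening and baseline were one visit, the totals would be 6 and 2. Neither matches.

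**Step 2: what does each visit supply (vapers)?**

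| Visit | MCC | Sputum | 12 h abstinence stated |
|---|---|---|---|
| 1 Screening | none | yes, decides eligibility | no |
| 2 Baseline | 120-minute scan | yes | yes |
| 3 About 24 h later | 30-minute follow-up scan | yes | no |
| 4 and 6 Test days | 120-minute scan after vaping | yes, after the scan | yes |
| 5 and 7 Next day | 24 h scan | yes | no |

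**Step 3: MCC.** The primary endpoint averages clearance from 10 to 120 minutes. Before any study vaping, only visit 2 supplies that. The visit 3 scan is short and belongs to the same isotope dose. The rule cannot be followed literally, but only one scan can be meant.

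**Step 4: sputum.** Three samples precede any study vaping (visits 1, 2 and 3). The literal rule picks visit 1. Let S be the screening value, B the baseline-visit value, and Y_A, Y_B the post-vaping values under the two regimens.
- Effect on μA: mean(Y_A − S) − mean(Y_A − B) = mean(B − S). The effect on μB is the same.
- Effect on the contrast in a subject with both periods: (Y_A − S) − (Y_B − S) = Y_A − Y_B, whichever reference is used.

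The documents give no information on mean(B − S), so neither its size nor its sign is known. The abstinence mismatch concerns the test-day samples (visits 4 and 6). The next-day samples (visits 5 and 7), like the screening sample, have no stated abstinence.

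**Step 5: late sputum.** From the end of vaping, 10 minutes' wait + under 5 minutes' isotope inhalation + 120 minutes' scan = at most 135 minutes, or 2.25 h. Counted from vaping, the late sample falls at about 24 h. Counted from the end of the scan, it falls at about 24 + 2.25 = 26.25 h. Neither is 48 h, and the seven visits leave no other day.

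**The case against.** The best defence is that the protocol uses the two terms loosely. The procedures subsection has a heading that joins screening and baseline, and its first sentence speaks of them as one visit. On that view, Section 5.3 uses the screening visit as shorthand for everything before randomisation, and since the Synopsis and Section 3.1 already treat the baseline-visit sputum as baseline, an analyst would choose correctly. This is a plausible account of how the wording arose, and for MCC it settles the matter. It does not settle sputum: three pre-vaping samples exist, the rule names one of them, and the choice should not be left until data are in hand.

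A second objection is that selection on the screening sputum need not cause regression to the mean. The Synopsis describes the requirement as enough viable cells for analysis. If later samples must meet the same threshold, the selection effect is zero. This objection stands. The documents do not say whether later samples face that threshold, and give neither a screen-failure rate nor a correlation between cell yield and the endpoints.

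Third, only two post-vaping sputum samples are scheduled per session, so the one labelled 48 h can only be the next-day sample. That also stands.

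A reader might infer more: that the primary MCC analysis is invalid, that the comparison of CA with no CA is biased, or that 48 h data will be missing. The documents support none of these. The intended MCC scan is clear, the common baseline cancels in subjects with both periods, and the model terms map onto a sample that is scheduled.

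**Conclusion.** The point holds as a minor inconsistency between the analysis rule and the schedule. For MCC it is a wording error with no effect on results. For sputum, a literal reading would shift both μA and μB by the mean difference between the baseline-visit and screening samples. The size and direction of that shift cannot be determined from the documents, and any part due to regression to the mean is zero if later samples must meet the same adequacy threshold.

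The randomised contrast is exactly unaffected only in subjects with both periods. Subjects who contribute one period to the mixed model are the exception; Section 5.4 anticipates 10% incompletion, and Section 3.8 replaces withdrawals. The stated sample sizes and powers do not depend on which visit supplies the baseline. The 48 h label is an error that causes no bias.

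The conclusion rests on reading screening and baseline as separate visits, which the visit totals confirm, and on taking the absence of an abstinence statement at screening at face value.

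**What to change.** In Section 5.3:
1. Define baseline for the Stage 2 MCC and sputum outcomes as the value from the baseline (MCC) visit, not the screening visit.
2. Note that a further pre-vaping sputum is taken about 24 h after the baseline visit, and state whether it serves as a reference, for example for the next-day post-vaping sample, or is not used.
3. Say how a subject with an inadequate baseline-visit sputum is handled, since that subject would lack a reference value.
4. Reconcile the 48 h label, in the immune cell model's text and in its table, with the sampling schedule.

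The cost is a few sentences. Every sample concerned is already scheduled, so no visit, procedure or subject is added.

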5.2 Exploratory Endpoints

Exploratory Endpoints include:

- Inflammatory Cell Expression in Epithelial Lining Fluid.
- CA-induced changes in immune cell function
- Peripheral Blood Mononuclear Cell Analysis
- Expression of inflammatory mediators in Blood Serum
- Pulmonary Mechanics with subjects own e-cigarette device
- Pulmonary Mechanics with investigator e-cigarette device
- CA-Induced changes in Epithelial Lining Fluid
- Peripheral blood mononuclear cell analysis

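### No Stage 2 model uses the pre-vaping nasal ELF sample taken in each period; the single earlier baseline gives the CA contrast no precision and leaves weeks of between-visit variation in the per-regimen changes

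*Combined protocol and SAP*

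**What the plan says.** The intervention procedures (section 3.5, by visits) place an ELF collection ahead of the exposure: "After vital signs, baseline spirometry, urine, and ELF collection, subjects will vape with the randomized e-liquid, either with or without CA". ELF is taken again after the scan ("subjects will undergo MCC scan for 120 minutes followed by immediately by vital sign collection, ELF collection, spirometry, and IS") and once more the next day. The whole session is then repeated: "There will a 2-6 week washout, and the subject will return to repeat the session, vaping the crossover e-liquid". Each period therefore has its own pre-vaping, post-scan and 24-hour ELF values.

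Section 5.3 sets one rule, stated for every outcome with total MCC as the example: "the dependent variable will be the post-vaping change from the baseline value that was obtained during the screening visit". It then fits the crossover model separately to each outcome of interest and lists the two regimen means, μA and μB, beside their difference among the parameters to be interpreted.

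The screening procedures list no ELF. The first ELF sample comes afterwards, when subjects who pass screening "return to the study lab and undergo a baseline MCC, 40cc of blood collection, epithelial fluid lining collection (ELF), urine collection". Section 5.2 lists "CA-Induced changes in Epithelial Lining Fluid" as an exploratory endpoint.

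**The concern.** Mucociliary clearance (MCC) and induced sputum have no pre-vaping measurement on session days, so an earlier baseline is the only one available for them. ELF is different: the procedures provide a same-day value in both periods, and the analysis section gives it no role. Two things are at stake for the ELF endpoint. The CA contrast forgoes a covariate that could sharpen it in a trial of about 20 completers. The per-regimen changes are measured across weeks although a same-day reference exists. There is also a wording problem: read literally, the rule points to a visit at which no ELF is listed. If the choice of ELF baseline is not fixed before unblinding, it becomes a post hoc choice.

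**Working it through.** **Plan's own figures.** The documents give no variance, correlation, sample size or power for any ELF outcome, so there is no ELF figure to reproduce. The number of completers, n = 20, comes from the MCC calculation in section 5.4. The paired normal approximation gives [7.0 × (1.960 + 0.8416) / 4.5]² = 18.99, so 19, close to the stated 20. It is used below only for the cost of estimating a slope.

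**Time gaps.** From the baseline visits to session 1: 2–6 weeks. To session 2: (2 + 2) to (6 + 6) = 4–12 weeks. Across both periods the ELF change therefore spans 2–12 weeks. A same-day change to the post-scan sample would span about an hour of vaping, a 10-minute wait, the isotope inhalation and a 120-minute scan.

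**What the shared baseline does to the contrast.** For a subject with both periods, (Y2 − Y0) − (Y1 − Y0) = Y2 − Y1. The baseline Y0 drops out. The covariate β{Y(t0) − mean} in section 5.3 takes the same value in both periods, so it drops out too. The contrast μA − μB is the one that the post-vaping values alone would give: unbiased by the baseline, and no more precise for it.

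**What a period-specific covariate could add.** Assume equal variances s², within-day correlation rs and between-visit correlation rb.
- Variance of the post-vaping difference between periods: 2s²(1 − rb). The pre-vaping difference has the same variance.
- Covariance of the two differences: 2s²(rs − rb), so their correlation is (rs − rb)/(1 − rb).
- Variance ratio with the covariate: 1 − [(rs − rb)/(1 − rb)]². Example: rs = 0.7, rb = 0.5 gives 1 − (0.2/0.5)² = 0.84.
- Approximate cost of estimating the slope: 1 + 1/(n − 4) = 1 + 1/16 = 1.0625.
- Variance ratio for a plain same-day change score: 2(1 − rs)/(1 − rb).

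| rs (rb = 0.5) | Covariate | Covariate × 1.0625 | Same-day change score |
|---|---|---|---|
| 0.6 | 0.96 | 1.02 | 1.60 |
| 0.7 | 0.84 | 0.89 | 1.20 |
| 0.8 | 0.64 | 0.68 | 0.80 |
| 0.9 | 0.36 | 0.38 | 0.40 |

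The shared baseline stands at 1.00 throughout. At rb = 0.3 the covariate ratios become 0.82, 0.67, 0.49 and 0.27 (for example, 1 − (0.3/0.7)² = 0.82). At a fixed rs, a between-visit correlation above 0.5 shrinks the gain.

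**What the baseline does to the per-regimen changes.** Let r be the share of within-subject variance common to samples from one day, r = (rs − rb)/(1 − rb). Moving to same-day baselines multiplies the SD of a change score by √(1 − r): 0.89, 0.71 and 0.45 at r = 0.2, 0.5 and 0.8. For mean drift, assume 0.05 within-subject SD per week and the 4-week midpoint of the first gap. Then μA and μB both shift by 0.05 × 4 = 0.20 SD under the single baseline and by 0.00 under same-day baselines. Further average drift between the periods goes into the period effect π. A simulation of the crossover (n = 20, 20,000 replicates, true contrast 0.50) returned 0.50 under both choices, with the 0.20 shift in each regimen mean under the single baseline only.

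**The case against.** **Scope.** The sentence that introduces the Stage 2 models names only MCC and sputum endpoints, and Aims 2a and 2b cover only those. The change-from-baseline rule may not have been meant for ELF. This stands in part: applying it to ELF rests on the every-outcome wording. On the narrower reading, however, ELF has no specified analysis at all, and the pre-vaping samples still have no stated use. The alternative mixed model at the end of section 5.3, which is to use all data together, names no same-day baseline and is too general to fill the gap.

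**Bias.** A reader might infer that weeks of drift bias the CA versus no-CA comparison. The documents do not support that: the shared baseline cancels, and average drift between periods is absorbed by π.

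**Drift is already limited.** Section 3.1 asks vapers to keep their habits stable and keep a diary, and the unscheduled-visits section requires unrelated illness, such as a respiratory infection, to resolve before it can interfere with data. This reduces two sources of drift, but not ordinary day-to-day or seasonal nasal variation.

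**Pre/post change as the CA effect.** A reader might take the same-day change under the CA liquid as the acute effect of CA. It also contains vehicle, nicotine, time of day and repeated nasal sampling, and section 5.4 itself allows that the liquid without CA may be active. Only the between-regimen contrast isolates CA.

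**Reach.** ELF is not the only pre-vaping sample in each period, since urine is collected then too. Spirometry is also measured before vaping, but it is not a listed endpoint, so the point does not extend to it. Nor does it extend to MCC or sputum. Finally, the synopsis mentions ELF on session days only after the scan and the next day, so the pre-vaping sample rests on section 3.5.

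**Conclusion.** The point holds as a gap in pre-specification for one exploratory endpoint. Pre-vaping ELF is scheduled in both periods, and nothing in section 5.3 uses it. The randomised contrast is not biased. What is lost is possible precision in that contrast and a clean reference for μA and μB, which as written carry 2–12 weeks of between-visit variation.

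The size depends on correlations that the documents do not give. With rb = 0.5 and after the slope cost, the contrast variance would fall by about 11% at rs = 0.7, 32% at 0.8 and 62% at 0.9, and would not fall at 0.6. The 24-hour sample is not same-day, and no abstinence is stated before that visit as it is before the sessions, so its gain is likely smaller. The drift figure of 0.20 SD is an illustration under an assumed rate. No primary or secondary conclusion is affected, so priority is low.

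**What to change.** In section 5.3, for ELF only, state before unblinding that:
- the post-scan and 24-hour ELF values are modelled with that period's own pre-vaping ELF value as a covariate, entered for example as the within-subject difference between the two periods' pre-vaping values, on the same transformed scale as the outcome;
- the CA effect is the between-regimen contrast from that model;
- same-day pre/post changes may be tabulated per regimen as descriptive changes, and are not labelled as the CA effect.

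Prefer the covariate to a plain same-day change score, which loses precision for the contrast when r is below 0.5 (ratios 1.60 and 1.20 in the table). Keep the single earlier baseline for MCC and sputum. Reconcile the reference to the screening visit with the procedures, which list the first ELF at the later baseline MCC visit, and reconcile the synopsis with section 3.5 on the pre-vaping collection.

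The cost is wording plus one extra model parameter (one per time point if the two are modelled separately). No new samples or procedures are needed if section 3.5 describes what is done.
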